#### SAP and protocol version:

SAP version and date:	SIM-Study SAP v. 1.0 23.10.2023
Protocol version	This document has been written based on information contained in the study protocol version 1.1.1 , 18.11.22

#### SAP revision history:

Protocol version	SAP version	Section number changed	Description and reason for change	Date changed

## **STATISTICAL ANALYSIS PLAN for SIM-study**

---

**ABBREVIATIONS**

AE	Adverse Event
ATC	Anatomical/Therapeutic/Chemical
CI	Confidence Interval
DMC	Data Monitoring Committee
eCRF	electronic Case Report Form
EDC	Electronic Data Capture
MedDRA	Medical Dictionary for Regulatory Activities
SAE	Serious Adverse Event
SAS	Statistical Analysis System
SD	Standard Deviation
DAE	Discontinuation due to Adverse Event
EC	Ethics Committee, synonymous to Institutional Review Board (IRB) and Independent Ethics Committee (IEC)
GCP	Good Clinical Practice
IMP	Investigational Medicinal Product (includes active comparator and placebo)
IND	Investigational New Drug
SOP	Standard Operating Procedure
ESAS	Edmonton symptom assessment scale
HRQoL	Health-related quality of life
EORTC QLQ-C30	European Organization for Research and Treatment of Cancer Quality of life questionnaire - 30 items
SC	Subcutaneous
IV	Intravenous
PCA	Patient-controlled analgesia
NRS	Numeric rating scale
OME	Oral Morphine Equivalent

## 1 Introduction

### 1.1 Background and Rationale

Adherence to the WHO analgesic ladder has in validation studies provided pain relief to the majority of patients with cancer pain (Ventafridda et al., 1985). However, it is well established that some patients need parenteral administration of opioids to achieve adequate pain (Radbruch et al., 2011). For the combination of continuous infusions and bolus doses of morphine, both the subcutaneous (SC) and intravenous (IV) routes have proven feasible and effective. However, few direct comparisons of the intravenous and subcutaneous routes have been performed (Radbruch et al., 2011). Thus, it is not known whether any of the two routes should be preferred as the first-line option when initiating parenteral opioid infusion combined with bolus doses of opioids (Caraceni et al., 2012).

### 1.2 Intervention(s)

Palliative care cancer patients with unsatisfactory pain control despite oral or transdermal opioid titration where opioid rotation to parenteral morphine is clinically indicated can be included in the study. Study participants will start morphine infusion via a patient-controlled analgesia (PCA) pump intravenously or subcutaneously. The study drug is Morphine diluted with normal saline to 5 mg/ml or 10 mg/ml in 100 ml drug containers suitable for CADD Solis PCA pump.

#### 1.2.1 Brief description of the study intervention

The patient will have two PCA pumps. One connected to an IV line, one connected to a SC line. One infusion pump contains study drug (Morphine), one pump normal saline. Infusion rate and bolus doses are titrated equally from the two PCA pumps. The allocation procedure is randomized with a 1:1 ratio. Blinding is performed by the pharmacy producing the drug containers. Patients, staff, and study personnel are blinded during the 48-hour intervention period (Double-blinded, double-dummy study).

#### 1.2.2 Control settings (if applicable)

All participants receive study drug (Morphine) either IV or SC. Comparisons will be performed between the two routes of administration. There will be no patients receiving only placebo and comparison to placebo is not part of this study.

### 1.3 Trial Objectives

The overall objective is to establish whether either the IV or SC route of administration has clinically significant advantages when parenteral administration of morphine is started with a combination of continuous infusion and bolus doses in palliative cancer patients.

#### 1.3.1 Main study

### 1.3.1.1 Primary research question

- a) Is there a difference between SC and IV administration of morphine in how quickly pain control is achieved after initiation of a continuous infusion?

### 1.3.1.2 Secondary research questions

- b) Is there a difference in number of bolus doses after 24 and 48 hours between the groups
- c) Is there a difference in pain score (NRS 0-10) between the groups
- d) Is there a clinically significant difference between SC and IV administration of morphine in time from administration of bolus dose to clinically significant pain relief?

### 1.3.1.3 Pharmacokinetic study research question

- e) What is the difference in the key pharmacokinetic parameters  $T_{max}$ ,  $C_{max}$ , and  $AUC_{0-60}$  after SC and IV administration of morphine bolus doses during morphine infusion in palliative cancer patients?

### 1.3.2 Exploratory research question (if applicable)

Exploratory objectives include but are not restricted to following research questions:

- i. Are there any group differences in change of ESAS score other than pain?
- ii. What is the Patient Global Impression of Change in the two groups?
- iii. Is there a difference between SC and IV group in morphine concentration in steady state\*?  
(\*>24 hours after start of infusion and >2 hours since last bolus dose)
- iv. Is there a relationship between BMI and pharmacokinetic analyzes in the SC group?
- v. How does respiration frequency (RF) and oxygen saturation change during the intervention?  
Are there any differences between the SC and IV group?
- vi. What is the change in opioid side effect score in the two groups at 0, 24 and 48 hours
- vii. What is the change in opioid dose (in OME) from start of titration to 48 hours
- viii. What is the change in opioid dose (in OME) during follow up period
- ix. What are the complications to SC line and IV line
- x. What is the study population survival censored at 4 weeks

## 2 Trial Methods

### 2.1 Trial Design

Comparison of morphine infusion combined with bolus doses, administered subcutaneously or intravenously. The study is a single center phase III randomized controlled double blind, double dummy trial with open label follow-up.

In order to ensure blinding during the double-blind phase of the study, each participant will have both an intravenously and a subcutaneously administered PCA pump. One pump will contain morphine, the other placebo (saline).

The intervention period is 48 hours

Open label follow-up is four weeks

### **2.2 Randomization**

The allocation ratio between treatments is 1:1 with no stratification. The randomization will be performed by using a computer-generated list of blocks of 6-8 patients. The randomization process is described in detail in *SIM-Study Procedure Manual version 1.3, 07.07.22*. Details of the randomization including the final random allocation list are held securely and unavailable to unauthorized trial personnel. Sequentially numbered, opaque, sealed envelopes containing information about patient allocation are located at the Department of Palliative Medicine for emergency and unblinding after 48-hour intervention period.

### **2.3 Statistical Framework**

This trial is designed to establish the superiority of IV morphine PCA infusion compared to SC PCA infusion. The primary null hypothesis is that there is no difference in time from start of PCA infusion to last dose titration. The alternative hypothesis is that the time from start of infusion to final infusion rate titration differs between the two groups.

### **2.4 Hypothesis Test**

#### ***2.4.1.1 Null-hypothesis:***

##### **Primary**

- a. There is no difference in time from start of a PCA pump until a titrated infusion rate that gives a clinically significant reduction in pain in the SC and IV group.

##### **Secondary**

- b. There is no difference in number of bolus doses from PCA in the SC and IV group.
- c. There is no difference in pain score as assessed by NRS for the whole 48-hour period
- d. There is no difference in time from administration of a bolus dose to decrease in pain (change of 2 on 0-10 NRS) intensity and to acceptable pain relief between the SC and IV groups.

##### **Pharmacokinetic study**

- e. There is no difference in  $T_{max}$ ,  $C_{max}$ , and  $AUC_{0-60}$  between the SC and IV groups

#### ***2.4.1.2 Alternative hypothesis***

---

## **STATISTICAL ANALYSIS PLAN for SIM-study**

---

### **Primary**

- a. The time from start of infusion to final infusion rate titration differs between the SC and IV groups

### **Secondary**

- b. The number of bolus doses after 24 and after 48 hours in the two groups are different
- c. The pain score in the groups differ during the 48-hour period
- d. Time from bolus dose to clinically significant pain relief (change of 2 on 0-10 NRS) differ between the SC and IV group

### **Pharmacokinetic study**

- e. There is a difference in  $T_{max}$ ,  $C_{max}$ , and  $AUC_{0-60}$  between the SC and IV groups

#### **2.4.2 Confidence Intervals and p-values**

All calculated p-values will be two-sided. The differences between the groups will be considered significant for p-values less than 0.05. All efficacy estimates will be presented with two-sided 95% confidence intervals. As there is only one primary null hypothesis to be tested in this trial, there will be no adjustments for multiple testing.

#### **2.4.3 Decision Rule**

This trial is designed to address a single primary outcome. Superiority is claimed if the primary null hypothesis is rejected on the significance level (alpha) of 0.05 (two-sided). That is, the 95% confidence interval of the difference between the two groups does not include zero.

## **2.5 Timing of Outcome Assessments**

For all clinically planned measures, visits should occur within a window of the scheduled visit as described in Table 1. The exact time of a visit is also recorded.

Time of bolus titrations and time of bolus doses are registered with exact time.

**Table 1 Schedule of assessment**

Time	Screening Period	Treatment Period		
	Within 24 hours of treatment	Baseline/start of treatment Between 11 am and 3 pm	12, 24, 36, and 48 +/- 2 hours	24 +/- 2; 48 +/- 2 hours
Informed consent	X			

## STATISTICAL ANALYSIS PLAN for SIM-study

---

Time	Screening Period	Treatment Period		
	Within 24 hours of treatment	Baseline/start of treatment Between 11 am and 3 pm	12, 24, 36, and 48 +/- 2 hours	24 +/- 2; 48 +/- 2 hours
Inclusion/exclusion Evaluation	X			
Height, Weight	X			
Medical History	X			
Prior analgesic treatment	X			
Current medication	X			
Vital signs		X	X	
ESAS-revised		X	X	
EORTC QLQ-C30		X		X(at 48 +/- 2 hours)
EAPC basic data set	X			
Opioid side effects		X		X
Patient Global Impression of Change				X (at 48 +/- 2 hours)
Blood samples 	X			
Treatment administration/dispensation		X	X	
Adverse event		X	X	X
Clinician's decision to continue ongoing treatment or to change treatment				X
Record of concomitant medication		X	X	X
Morphine dose		X	X	X
Hospitalization				
Survival				
Complications to IV line				
Need for switch SC to IV				
Reason for withdrawal				

1. Blood pressure, pulse, temperature, sedation level, respiratory rate

2. CRP, Hb, WBC (incl. differential counting), PLT, Na, K, Ca, creatinine, ASAT, ALP, γGT, INR, albumin, bilirubin

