## **5 Safety Analyses**

The number (and percentage) of patients experiencing each AE/SAE will be presented for each treatment group categorized by severity. For each patient, only the maximum severity experienced of each type of AE will be displayed. The number (and percentage) of occurrences of each AE/SAE will also be presented for each treatment arm.

The Data Monitoring and Safety Committee (DMSC) will be informed of serious adverse events. The committee will if necessary, make decisions about terminating the trial before completed inclusion.

Study-specific safety measurement during intervention period:

Repeated measurement of saturation (every 12 hours), sedation level and respiration frequency (every 2 hour and after each bolus dose) will be assessed by linear mixed models mirroring the approach used for the analysis of secondary outcome c).

Opioid side effects score, mean (SD) at 24 and 48 hours will be presented for each treatment group and compared by an independent samples t-test

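### Question ix asks about complications of both lines, but Table 1 has a dedicated row for the IV line only and no planned safety table is split by line

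*SAP*

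**What the plan says.** Section 1.3.2 of the SAP, item ix, poses the exploratory question "What are the complications to SC line and IV line". Both lines are named.

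The schedule of assessments (section 2.5, Table 1) has one row for line problems, "Complications to IV line". There is no matching SC-line row. The schedule also has a general adverse event row, marked in all three treatment-period columns and not tied to either line.

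Section 2.1 says that, for blinding, "each participant will have both an intravenously and a subcutaneously administered PCA pump". Section 1.2.1 says the same of the lines: "One connected to an IV line, one connected to a SC line". One pump holds morphine and the other saline.

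On reporting, section 5 states: "The number (and percentage) of patients experiencing each AE/SAE will be presented for each treatment group categorized by severity". Section 5.1 adds summaries by system organ class and preferred term (by group and overall), for severe events and for events leading to discontinuation, with sub-tabulations by diagnosis. None of these is split by SC or IV line, or by what the line carried.

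**The concern.** The trial's overall objective (section 1.3) is to find out whether either route has clinically significant advantages. Complications of the line are a harm specific to route, and question ix shows that the authors meant to describe them for both lines.

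Two features of the plan work against that. First, one line has its own row and the other depends on someone reporting an adverse event. Unequal ascertainment can by itself produce a difference between lines, or hide one. Second, in the double-dummy phase the randomised arm says which line carries morphine, not which line the patient has. A reaction at the saline SC site of an IV-arm patient is counted in the IV arm, and a problem with the saline IV line of an SC-arm patient is counted in the SC arm. Similar totals in the two arms could then be taken to mean that the lines are equally safe, which such totals do not show.

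**Working it through.** The SAP gives no figure for line complications, so there is none to reproduce. The check sets the sections side by side and then works out what an arm-level total can show.

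**Text comparison**

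| Place in SAP | SC line | IV line |
|---|---|---|
| 1.3.2, question ix | named | named |
| 2.5, Table 1, dedicated row | absent | present |
| 2.5, Table 1, general adverse event row | possible | possible |
| 5 and 5.1, tables split by line | none | none |

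**What an arm-level total measures.** Let IVm, IVs, SCm and SCs be the expected line events per patient for an IV or SC line carrying morphine (m) or saline (s). From sections 1.2.1 and 2.1:

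- IV arm: IVm + SCs
- SC arm: SCm + IVs
- Difference, IV arm minus SC arm: (IVm + SCs) − (SCm + IVs) = (IVm − IVs) − (SCm − SCs)

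The main effect of line type cancels. What remains is how far the effect of morphine against saline differs between the two lines. If the fluid does not matter (IVm = IVs and SCm = SCs), the difference is 0 − 0 = 0 for any pair of line risks.

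**Illustration with assumed risks.** The SAP gives no risks. Assume that 20% of SC lines and 10% of IV lines have a complication, independently and whatever the fluid. Patients with at least one line complication:

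- IV arm: 1 − (1 − 0.20)(1 − 0.10) = 1 − 0.72 = 28%
- SC arm: the same product, 28%
- Difference between arms: 0; difference between lines: 20% − 10% = 10 points

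Swapping the assumed risks (SC 10%, IV 20%) again gives 1 − 0.90 × 0.80 = 28% in both arms, so the arm totals do not even show which line is worse. More generally, 1 − (1 − p)(1 − q) is the same in both arms for any risks p and q. The equality of the arms does not need independence either. It needs only that the joint risk at the two lines is the same in both arms.

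**What a by-line count would use.** Section 4.9 plans 30 patients per group, so up to 2 × 30 = 60 patients, each with one SC and one IV line, giving up to 60 within-patient pairs. Under the assumed risks, expected counts are 0.20 × 60 = 12 SC lines and 0.10 × 60 = 6 IV lines with a complication. By arm, 0.28 × 30 = 8.4 patients would be expected in each.

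**The case against.** The case on the other side has real force on several points.

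- **SC events are not excluded.** A reader might infer from Table 1 that only IV-line complications will be recorded. The SAP does not support that: question ix names both lines, and adverse event recording is open to either. What stands is a mismatch between two sections and unequal dedicated recording.
- **Preferred terms may reveal the site.** A reader might infer that the safety tables cannot distinguish the lines. That is too strong. If SC-site and IV-catheter events are coded under different terms, the example above would give rows of about 20% and 10% within each arm, and the line difference would be visible. But the SAP does not require such coding and plans no by-line summary.
- **The 28% is a composite that the SAP does not name**, and the equality assumes that the fluid has no effect on line risk. If morphine changes local reactions, the arms can differ, but the contrast would then reflect the fluid effect and still not the line effect.
- **The row may belong to open-label follow-up.** It has no mark in any column shown and stands among items such as survival and hospitalisation. Section 2.1 says "Open label follow-up is four weeks", and a follow-up column may have been lost when the table was read. The blank cells are therefore not counted as an error. Even so, there is no SC-line row for that period either.
- **Tabulating by arm is not wrong.** It is the direct randomised comparison of the route of morphine, and it suits systemic events.
- **The switch row runs only from SC to IV.** A reader might call this a second asymmetry. Section 4.5 describes only SC-to-IV conversion, so the row agrees with the rest of the SAP.
- **Question ix is exploratory.** Section 4.8 sends unspecified analyses to a separate plan, and the protocol and procedures manual, not seen here, may already provide for SC-line recording. This limits the weight of the point. It does not remove the contradiction within the SAP.

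**Conclusion.** The point holds in a limited form. The SAP asks about complications of both lines, gives only the IV line a dedicated row, and plans no summary by line although every patient has both during the blinded 48 hours. An arm-level total of line events is not a comparison of SC with IV lines. Its expected difference is exactly zero when line risk does not depend on the fluid, and otherwise reflects a difference in fluid effects. The zero follows from the design; the 28% and the 10 points are illustrations resting on assumed risks and independence.

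This is an exploratory and safety matter of minor to moderate weight. It has no bearing on the primary analysis or the sample size.

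**What to change.** 1. Reconcile Table 1 with question ix: have the schedule name both the SC line and the IV line, with complications recorded separately for each.
2. In section 5, add one descriptive table of line-related events for the 48-hour phase, by line (SC or IV) and content (morphine or saline), with SC and IV compared within patient.
3. For open-label follow-up, tabulate line-related events by the route in use. Section 4.5 foresees conversion from SC to IV in that period, so the randomised arm may no longer match the route.
4. Keep the by-arm tables for systemic events.

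The cost is slightly more data entry (one field for the SC line if the eCRF does not already have it) and one extra table. No additional visit or patient is needed, and the by-line comparison stays descriptive.

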## 2.6 Statistical Interim Analysis and Stopping Guidance

---

There will be no interim analyses in this trial. The Data Monitoring and Safety Committee (DMSC) will recommend stopping the trial if there is a safety concern.

[figure not shown]
## **2.7 Timing of Main Analysis**

The main analysis is planned when all patients have completed the 48-hour intervention period. Pharmacokinetics will be analyzed when morphine serum concentration is measured for 20 study participants.

### 3 Trial Population

#### 3.1 Screening Data, Eligibility, and Recruitment

The “CONSORT” diagram comprises the number of people screened, eligible, consented, randomized, receiving their allocated treatment, and withdrawing/lost to follow-up.

### 3.2 Baseline Patient Characteristics

Baseline characteristics (Tests of statistical significance will be performed for baseline characteristics but not included in the baseline tables in the article reporting the results; rather, the clinical importance of any imbalance between the two groups will be noted. The final table may be adjusted or abridged according to manuscript guidelines in the respective journal.

**Table 2**) will be summarized by treatment group and overall using descriptive statistics. Categorical data will be presented by numbers and percentages. Continuous data will be summarized by means, standard deviations (SDs), and min-max values if data are symmetrically distributed, and median, min-max values, and quartiles for skewed data. Tests of statistical significance will be performed for baseline characteristics but not included in the baseline tables in the article reporting the results; rather, the clinical importance of any imbalance between the two groups will be noted. The final table may be adjusted or abridged according to manuscript guidelines in the respective journal.

**Table 2 Baseline characteristics**

Characteristics	IV (n=xx)	SC (n=xx)	Overall (n=xx)
Age, mean/median (SD, min-max)/(min-max,Q 1 -Q 3 )			
Sex Female, n (%)			
Performance status Karnofsky, median (min-max, Q 1 -Q 3 )			
ESAS, baseline For each element mean (SD, min-max)			
EORTC-QLQ c 30, baseline Function, mean (SD, min-max)			
Global health, mean (SD, min-max)			
Symptom burden, mean (SD, min-max)			
Weight, mean (SD, min-max)			
Height, mean (SD, min-max)			
BMI, mean (SD, min-max)			
Years with principal cancer diagnosis, median (min-max,Q 1 -Q 3 )			
Metastatic situation	n (%)	n (%)	n (%)
Localized/locally advanced disease only			
Metastatic disease			
Cancer diagnosis	n (%)	n (%)	n (%)
Malignant neoplasms of digestive organs			
Malignant neoplasms of respiratory and intrathoracic organs			
Malignant neoplasms of urinary tract			
Malignant neoplasms of male genital organs			
Malignant neoplasm of breast			
Malignant neoplasms of female genital organs			

## STATISTICAL ANALYSIS PLAN for SIM-study

---

Characteristics	IV (n=xx)	SC (n=xx)	Overall (n=xx)
Malignant neoplasms of ill-defined, secondary and unspecified sites			
Melanoma and other malignant neoplasms of skin			
Malignant neoplasms of eye, brain and other parts of central nervous system			
Malignant neoplasms, stated or presumed to be primary, of lymphoid, hematopoietic and related tissue			
Malignant neoplasms of lip, oral cavity and pharynx			
Malignant neoplasms of mesothelial and soft tissue			
Malignant neoplasms of bone and articular cartilage			
Malignant neoplasms of thyroid and other endocrine glands			
Any ongoing anti-cancer treatment	n (%)	n (%)	n (%)
Chemotherapy			
Immunotherapy			
Hormone therapy			
Radiotherapy			
Comorbidity	n (%)	n (%)	n (%)
Circulatory			
Musculoskeletal			
Endocrine			
Digestive			
Neurological			
Genitourinary			
Neoplasms			
Respiratory			
Behavioral			
Infection			
Eye			
Skin			
Blood			
Medication	n (%)	n (%)	n (%)
Non-opioid analgesics			
Opioids			
Antidiabetics			
Anticoagulants			
Antiepileptics			
Corticosteroids			
Antidepressants			
Antiemetics			
Neuroleptics			

